6.6.3 Clinical Laboratory Evaluations

Blood and urine samples for determination of clinical chemistry, haematology and urinalysis will be taken at the times indicated in the Study Plan (see section 6.1).

The following laboratory variables will be measured at local lab:

· · · · · · · · · · · · · · · · · · ·		
Haematology/Haemostasis (whole blood)	White bloo	d cell (WBC) count
	Red blood	cell (RBC) count
	Haemoglol	bin (Hb)
	Haematocr	it (HCT)
	Mean corp	uscular volume (MCV)
	Mean corp	uscular haemoglobin (MCH)
	Mean corp (MCHC)	uscular haemoglobin concentration
	Neutrophil	s absolute count
	Lymphocy	tes absolute count
	Monocytes	absolute count
	Eosinophil	s absolute count
	Basophils a	absolute count
	Platelets	
	Reticulocy	tes absolute count
Coagulation	International normalized ratio (INR)	
	Activated p	partial thromboplastin time
	(APTT)	
	Fibrinogen	
Clinical Chemistry* (serum or plasma)	Sodium	
Distribution:	Original:	Copy:
TPCA025 Version 2 (based on TPQA036 Version 2)		Effective Date: 27 th August 201 Prior Effective Date: 21 st December 201

Table 5: Clinical Laboratory Evaluation Panels

Sponsor:	AstraZeneca AB	Protocol/CIP Number:	D7550C00003	
CIL Project Number:	40343			
		Potassium		
		Urea		
		Creatinine		
		Albumin		
		Calcium		
		Phosphate		
		Glucose (fasting) (Not at Visit 1 - Screening)		
		Alkaline phosphatase (ALP) "LIVER PANEL"		
		Alanine aminotransferase (ALT) "LIVER PANEL"		
		Aspartate aminotransferase (AST) "LIVER PANEL"		
		Total bilirubin "LIVER PANEL"		
		TSH		
		Free T3		
		Free T4		
		Total T4		
Urinalysis		Glucose (dipstick)		
		Albumin (quantification/ser	mi-quantification)	
		Protein (dipstick)		
		Blood (dipstick)		
		WBC (Leukocytes) (dipstic	k)	
		Creatinine (quantification)		

*In case that ALT, AST>2ULN, ALP increase by 100%, bilirubin (total)>1.5ULN, intensified and extensive liver panel will be conducted.

Conversions to AZ preferred units will be applied where needed. Units and conversion factors are reported in the "Labcodes" version dated 16 May 2017 or higher. Laboratory measurements will be considered on treatment if they are collected from Day 1, after first dose of IP up to 7 days after the last dose of IP. Baseline value is defined in section 6.3.

Laboratory values will also be classified as normal (if value is within normal reference range) low (if value is below the low normal reference limit) or high (if value is above the high normal reference limit).

Potential Hy's law criteria will be assessed by total bilirubin, ALT and AST, as follow:

Parameter Criteria

Total bilirubin < 2xULN

Distribution:

Original:

Copy:

TPCA025 Version 2 (based on TPQA036 Version 2)

Sponsor:	AstraZenec	a AB	Protocol/CIP Number:	D7550C00003		
CIL Project Number: 40343						
	≥ 2xULN Total					
AT T.						
ALT	$> 3 - < 5 \times ULN$	< 3xULN > 3 - < 5xUILN				
	$\geq 5 - < 10 \text{xULN}$					
	≥10xULN					
	Total					
AST	< 3xULN					
	$\geq 3 - < 5 \text{xULN}$					
	$\geq 5 - < 10 \text{xULN}$					
	≥10xULN					
	Total					

Subject's highest on-treatment value will be used. Potential Hy's Law criterion is defined Aspartate Aminotransferase (AST) or Alanine Aminotransferase (ALT) ≥ 3x Upper Limit of Normal (ULN) together with Total Bilirubin (TBL) $\geq 2xULN$ at any point during the study following the start of study medication. The elevation in transaminases must precede or be coincident with (i.e. on the same day) the elevation in TBL, but there is no specified timeframe within which the elevations in transaminases and TBL must occur.

Urinalysis categorical variables will be classified as:

Parameter	Criteria		
Glucose	Neg 1+ 2+ 3+ 4+		
Albumin	0 1+ 2+ 3+ 4+ Trace		
Protein	Neg Trace +1 +2 +3 +4		
Blood	Neg Non-hem Trace Non-hem 2+ Hem Trace Hem 1+ Hem 2+		
TPCA025 Version (based on TPQA036		Original:	Copy: Effective Date: 27 th August 2017 Prior Effective Date: 21 st December 2016

Sponsor:	AstraZeneca AB	Protocol/CIP Number:	D7550C00003
CIL Project Number:	40343		

Hem 3+

WBC (Leukocytes) Neg 1 +2 +3+ 4+

6.6.4 **Other Observations Related to Safety**

Other observations related to safety will include Vital Signs, Electrocardiogram (ECG), Physical examinations, Body weight and BMI. Baseline values are defined as in section 6.3. Recordings are considered on treatment if they are collected from Day 1, after first dose of IP up to 7 days after the last dose of IP.

Vital Signs

Vital signs will include:

- Pulse rate (bpm),
- pulse oximetry (%), .
- systolic blood pressure (mmHg), .
- diastolic blood pressure (mmHg).

Vital signs will be obtained at time points indicated in section 6.1 (and ad-hoc as medically indicated). Pulse (beats/minute, radial artery, during 30 seconds) and pulse oximetry (%) will be measured before blood pressure and in a lying position after 10 minutes of rest. Thereafter, systolic and diastolic blood pressure (mmHg, the cuff method on the arm opposite to the one used for blood sampling) will be measured using the same cuff, appropriate for arm circumference, and in the same position, throughout the study. Subjects should be in the same position for the vital signs measurements throughout the study.

Change from baseline to each post-baseline measurement will be calculated as the postbaseline visit value minus the baseline visit value.

Electrocardiogram (ECG)

12-lead ECG recordings will be collected according to the assessments schedule presented in section 6.1. The investigator will make an overall evaluation of the ECG as normal, abnormal, abnormal non-clinically significant and abnormal clinically significant. Abnormal values shall not be recorded as AEs unless deemed clinically significant. Last observation on-treatment used for statistical analyses is the last available value among those in the On-treatment phase. If several measurements are collected on the last date (same day), the last on-treatment value will be the worst of the measurements collected during that day.

Physical Examination

A complete physical examination will be performed at Screening (Visit 1) and at Follow-up (Visit 5) and will include an assessment of the following: general appearance, respiratory, cardiovascular, abdomen, skin, head and neck (including ears, eyes, nose and throat), lymph Distribution: Original:

TPCA025 Version 2 (based on TPQA036 Version 2) Copy:

Effective Date: 27th August 2017 Prior Effective Date: 21st December 2016

Sponsor:	AstraZeneca AB	Protocol/CIP Number:	D7550C00003
CIL Project Number:	40343		

nodes, thyroid, musculoskeletal (including spine and extremities) and neurological systems. On the other occasions (Visits 2, 3, 4 and 4c) a brief physical examination (general appearance, skin, abdomen and musculoskeletal, cardiovascular and respiratory systems) will be conducted. Any new or aggravated clinically relevant abnormal medical finding at a physical examination as compared with the baseline assessment will be reported as an AE.

Physical examination will be determined by the investigator as normal, abnormal nonclinically significant and abnormal clinically significant.

Body Weight and BMI

Body weight and BMI will be collected according to the assessments schedule presented in section 6.1. Body weight assessments will be conducted in the mornings after an overnight fast (except for non-fasting at screening) with the subjects in underwear/light clothes and after a lavatory visit. Assessments are to be done on the same calibrated scale at all occasions. BMI is collected at screening only. For the purpose of the analyses BMI will be derived at each visit as: weight (kg) at visit / [height (m) at screening]², rounded to two decimal places.

Change from baseline to each post-baseline measurement will be defined as the postbaseline visit value minus the baseline visit value.

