Section 8.4.4([Exploratory biomarkers](#)): Removed GDF15, IL-1B and IL-6 from the list of exploratory biomarkers to be summarized statistically in the CSR, instead they will be referred to in an exploratory SAP and reported separately. This is based on a decision by the project team.

Version: 1.0 dated 5 July 2017

Initial creation

This Clinical Study Protocol has been subject to a peer review according to AstraZeneca Standard procedures. The Clinical Study Protocol is publicly registered and the results are disclosed and/or published according to the AstraZeneca Global Policy on Bioethics and in compliance with prevailing laws and regulations

CLINICAL STUDY PROTOCOL SYNOPSIS

A 12-week, randomized, single-blind, placebo-controlled, multi-centre, parallel group, phase IIa study to evaluate efficacy, safety and tolerability of oral AZD5718 after 4- and 12-weeks of treatment in patients with coronary artery disease (CAD)

International Co-ordinating Investigator:

[REDACTED]

Study site(s) and number of subjects planned

This study will be a multi-centre study conducted at approximately 10 centres in 3 countries. Approximately one hundred and thirty-eight (138 patients with coronary artery disease (CAD) will be randomized to ensure at least 66 evaluable patients receiving 12 weeks treatment with AZD5718 [REDACTED] or placebo. About 20% of the randomized patients will receive AZD5718 [REDACTED]. The patients on lower dose are included to guide dose selection in future studies. The study was originally designed to be a 4-week study and was amended to be a 12-week study. Therefore, the total number of patients is greater than required for a 12 weeks study (about 100), this since some patients will only have 4 weeks of treatment.

Study period

Estimated date of first patient enrolled Q4 2017

Estimated date of last patient completed Q1 2020

Phase of development:

Phase IIa

Study design

Randomized, single-blind, placebo-controlled, parallel-group, multicentre study in patients with CAD.

NB. The study was originally designed to be a 4-week study and was amended to be a 12-week study. As a consequence, some patients will have a treatment period of 4 weeks only while others will have a treatment period of 12 weeks.

Objectives

Primary Objective:	Outcome Measure:

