3.9 Discontinuation of investigational product

Patients may be discontinued from IP in the following situations:

- Patient decision. The patient is at any time free to discontinue treatment, without prejudice to further treatment
- An adverse event that, in the opinion of the Investigator or AstraZeneca, warrants discontinuation from further dosing
- Patient noncompliance that, in the opinion of the Investigator or sponsor, warrants withdrawal (e.g. refusal to adhere to scheduled visits)
- Patient is determined to have met one or more of the exclusion criteria or failed to meet all of the inclusion criteria for study participation at study entry and continuing IP, in the decision of the Investigator, might constitute a safety risk

If the patient is discontinued from IP, the scheduled study visits, data collection and procedures should continue according to the Clinical Study Protocol (CSP) until study closure. Alternatively, if the subject does not agree to this option, a modified follow up through e.g., regular telephone contacts or a contact at study closure should be arranged, if agreed to by the subject and in compliance with local data privacy laws/practices. The approach taken should be registered in the CRF.

If patient is required to or chooses to discontinue the IP, every reasonable effort should be made for the patient to remain in the study for follow-up and to complete all other study procedures until the scheduled end of the study.

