Study Day	-7 days	x^a	day 1	day 14	day 28	28 days after Visit 4	28 days after Visit 4b	28 days after last dose	
Time Window		1-5 days post ACS event	7-28days post ACS event	±2	±3	±2	±3	±4 days	
Informed consent (ICF)		x							
Inclusion/exclusion criteria		x	x						
Demographic data		x							Smoking history and alcohol consumption to be included
Height		x							
Body weight ^b		x	x	x	x		x	x	
Collect date for ACS event		x							
TIMI flow score		x							
Medical and surgical history		x							
Concomitant medication		x	x	x	x	x	x	x	

Table 1 Study assessment schedule

	ACS event	Visit 1 Screening	Visit 2 Randomization	Visit 3 (2 weeks) During Treatment	Visit 4 (4 weeks) During Treatment	Visit 4b (8 weeks) During Treatment	Visit 4c (12 weeks) End of Treatment	Visit 5 Follow-up	Comments
Study Day	-7 days	x ^a	day 1	day 14	day 28	28 days after Visit 4	28 days after Visit 4b	28 days after last dose	
Time Window		1-5 days post ACS event	7-28days post ACS event	±2	±3	±2	±3	±4 days	
Serology (see Table 3)		x							
FSH and luteinizing hormone (LH) sampling (females only)		x							
Randomization			x						
Diary card hand-out			x						
Diary card review				x	x	x	x		
Diary card hand-in							x		
IP dispensed			x		x	x			
IP returned					x	x	x		
IP intake at the clinic			x	x	x		x		
Safety and tolerability:									
Adverse event (AE) review		x (SAE only)	x	x	x	x ^m	x	x	

Table 1 Study assessment schedule

	ACS event	Visit 1 Screening	Visit 2 Randomization	Visit 3 (2 weeks) During Treatment	Visit 4 (4 weeks) During Treatment	Visit 4b (8 weeks) During Treatment	Visit 4c (12 weeks) End of Treatment	Visit 5 Follow-up	Comments
Study Day	-7 days	x ^a	day 1	day 14	day 28	28 days after Visit 4	28 days after Visit 4b	28 days after last dose	
Time Window		1-5 days post ACS event	7-28days post ACS event	±2	±3	±2	±3	±4 days	
Blood pressure and pulse rate (supine)		x	x	x	x		x	x	
12-lead pECG with electronic source file		x	x	x	x		x	x	
Physical examination ^c		x	x	x	x		x	x	
Blood and urine samples for safety laboratory evaluations (including fasting glucose) ^d		x ^{e,n}	x ^f	x ⁿ	x		x	x	
Efficacy Assessments:									
Spot urine for analysis of LTE ₄ levels and urinary creatinine		x ^l	x ^g	x (pre-dose)	x (pre-dose)		x(pre-dose)	x	Screening sample will not be used for assessment of primary endpoint

Table 1 Study assessment schedule

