Appendix D Actions Required in Cases of Increases in Liver Biochemistry and Evaluation of Hy's Law

1. Introduction

This Appendix describes the process to be followed in order to identify and appropriately report Potential Hy's Law (PHL) cases and Hy's Law (HL) cases. It is not intended to be a comprehensive guide to the management of elevated liver biochemistries.

During the course of the study the Investigator will remain vigilant for increases in liver biochemistry. The Investigator is responsible for determining whether a subject meets potential PHL criteria at any point during the study.

All sources of laboratory data are appropriate for the determination of PHL and HL events; this includes samples taken at scheduled study visits and other visits including central and all local laboratory evaluations even if collected outside of the study visits; for example, PHL criteria could be met by an elevated ALT from a central laboratory **and/or** elevated TBL from a local laboratory.

The Investigator will also review Adverse Event data (for example, for AEs that may indicate elevations in liver biochemistry) for possible PHL events.

The Investigator participates, together with AstraZeneca clinical project representatives, in review and assessment of cases meeting PHL criteria to agree whether HL criteria are met. HL criteria are met if there is no alternative explanation for the elevations in liver biochemistry other than Drug Induced Liver Injury (DILI) caused by the Investigational Medicinal Product (IMP).

The Investigator is responsible for recording data pertaining to PHL/HL cases and for reporting Serious Adverse Events (SAE) and Adverse Events (AE) according to the outcome of the review and assessment in line with standard safety reporting processes.

2. Definitions

Potential Hy's Law (PHL)

Aspartate Aminotransferase (AST) or Alanine Aminotransferase (ALT) $\geq 3x$ Upper Limit of Normal (ULN) **together with** Total Bilirubin (TBL) $\geq 2xULN$ at any point during the study following the start of study medication irrespective of an increase in Alkaline Phosphatase (ALP).

Hy's Law (HL)

AST or ALT $\geq 3x$ ULN **together with** TBL $\geq 2xULN$, where no other reason, other than the IMP, can be found to explain the combination of increases, e.g., elevated ALP indicating cholestasis, viral hepatitis, another drug.

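### The Hy's Law tables stop at last dose + 7 days, but the SAP and protocol Appendix D define the criterion over the whole study after first dose, so no in-window Visit 5 liver panel can enter them

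*SAP*

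**What the plan says.** SAP 6.6.3 assesses Potential Hy's Law from total bilirubin, ALT and AST and states that each subject's "highest on-treatment value will be used". Earlier in the section the period is fixed: "Laboratory measurements will be considered on treatment if they are collected from Day 1, after first dose of IP up to 7 days" after last dose.

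The sentence following the on-treatment rule defines the criterion as AST or ALT ≥3×ULN together with total bilirubin ≥2×ULN at any time in the study once medication has started. On sequence it says "The elevation in transaminases must precede or be coincident with (i.e. on the same day) the elevation in TBL", and on spacing "but there is no specified timeframe within which the elevations in transaminases and TBL must occur". Protocol Appendix D, section 2, uses the same open-ended period: "at any point during the study following the start of study medication irrespective of an increase in Alkaline Phosphatase (ALP".

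The planned outputs are Tables 14.3.7.8 (4-week cohort) and 14.3.7.9 (12-week cohort). Their titles attach the on-treatment qualifier to the ALT and AST maxima but not to the bilirubin maximum. SAP 8.10.3 repeats the cross-table at the second interim. SAP 5.2 lists other changes to the laboratory analyses but not this restriction.

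**The concern.** The rule for selecting values and the definition it is meant to serve cover different periods. A patient with ALT ≥3×ULN at Week 12 and bilirubin first ≥2×ULN at Visit 5 meets the definition, yet would not appear as a case when all three values are limited to the on-treatment period. These are the only tables in the SAP output list that cross ALT/AST with bilirubin, so a reader would take an empty cell to mean that no subject met the criterion.

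Two groups of panels are lost. One is every in-window Visit 5 panel. The other is any panel more than 7 days after an early stop of IP, because protocol 3.9 says that for such patients "the scheduled study visits, data collection and procedures should continue according to the Clinical Study Protocol (CSP) until study closure".

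A separate, smaller point is that crossing two maxima ignores the required order of the elevations. This can over-include subjects but cannot hide a case within the window.

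**Working it through.** The documents give no figure to reproduce here. The check compares days and then counts panels.

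**Inputs**
- On-treatment cut-off for laboratory data: last dose + 7 days (SAP 6.6.3).
- Visit 5: 28 ± 4 days after last dose (protocol 1.4 and Table 1). SAP Table 3 opens its window at last dose + 24.
- Safety panels after first dose, from the Table 1 row "Blood and urine samples for safety laboratory evaluations (including fasting glucose": Visits 3, 4 and 5 in the 4-week cohort; Visits 3, 4, 4c and 5 in the 12-week cohort. None is scheduled at Visit 4b. The liver panel is part of clinical chemistry (protocol Table 2).
- Cohort sizes: about 138 randomized in all, a total the Synopsis calls "greater than required for a 12 weeks study (about 100), this since some patients will only have 4 weeks of treatment". This gives about 100 twelve-week patients and 138 − 100 = 38 four-week patients.

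**Step 1: can Visit 5 enter the tables?** The in-window range is last dose + 24 to + 32. Against the cut-off, 24 − 7 = 17 and 32 − 7 = 25, so the panel falls 17 to 25 days too late. No in-window Visit 5 panel can enter.

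**Step 2: share of scheduled panels excluded, with full on-site attendance and no early stop**
- On-treatment panels: 38 × 2 + 100 × 3 = 376.
- Visit 5 panels: 38 + 100 = 138.
- Total: 376 + 138 = 514. Excluded: 138/514 = 26.8%.
- By cohort: 38/114 = 33.3% (1 of 3 per patient) and 100/400 = 25.0% (1 of 4 per patient).

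**Step 3: departures from that base case.** Let p be the share of Visit 5s held on site and q the number of 12-week patients whose last dose is on Day 28 but who keep all visits. Their Week 12 panel falls at last dose + 56 and is excluded. The excluded share is (138p + q)/(376 + 138p). SAP 5.2 confirms that some Visit 5s were by phone, but neither p nor q is given, so these are assumed examples:

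| p | q | Excluded |
|---|---|---|
| 1 | 0 | 138/514 = 26.8% |
| 0.5 | 0 | 69/445 = 15.5% |
| 1 | 10 | 148/514 = 28.8% |
| 1 | 20 | 158/514 = 30.7% |

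Phone visits lower the share and early stops raise it, so 26.8% is not an upper bound.

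**Step 4: where else a late case would be seen**
- *Final analysis.* Appendix D 4.2 requires an SAE report, Table 14.3.4.2 shows off-treatment SAEs, and SAP 8.8.3 lists all chemistry values.
- *Second interim (SAP 8.10.3).* By-visit chemistry stops at Visit 4c. The windows for Visits 3, 4, 4b and 4c require a date no later than last dose or last dose + 3, so nothing beyond + 7 can appear there. The only laboratory listing named is for urinalysis, and the AE and SAE tables are on-treatment only. A case whose AE starts after last dose + 7 would appear only in the AE listing. One whose AE starts on treatment and later becomes serious would count as an on-treatment SAE (SAP 6.6.2).

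**The case against.** The strongest reply is that the two passages do different jobs. Appendix D is a procedure for finding and reporting cases, while the SAP sentence governs a summary display and follows the on-treatment convention used for laboratory shifts elsewhere. Protocol 8.5.3 does not ask for a Hy's Law table, so no protocol-required analysis is being departed from. Case detection is also well protected: the investigator reviews each new laboratory report, a Potential Hy's Law case becomes an SAE, and the final outputs include key information on every SAE (Table 14.3.4.4) and off-treatment AEs by causality (Tables 14.3.2.11 and 14.3.2.12). The interims are administrative, and the safety committee's unblinded review is tied to the first one, which has no Hy's Law table. In the Week 12 example the subject would still sit in a row for ALT ≥3×ULN. Read literally, the table titles leave bilirubin unrestricted and would show that case.

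Much of this stands. At the final analysis the defect is confined to two tables, and no case goes unreported. It does not make the tables apply the criterion that they are titled as assessing. The SAP itself places the open-ended definition directly after the on-treatment rule, so the conflict lies within one document. The literal reading of the titles contradicts the SAP text, so two programmers could build different tables. Even on that reading, a case with both elevations first seen at Visit 5 is missed, because ALT and AST are restricted either way. By-visit chemistry at the final analysis shows Visit 5 values but does not pair ALT or AST with bilirubin within a subject.

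**Conclusion.** The concern holds. Followed as written, the SAP can produce Hy's Law tables showing no case when the collected data contain one that meets its own definition. Every in-window Visit 5 panel is excluded, as is any panel more than 7 days after an early stop of IP. The size is 26.8% of scheduled post-dose panels (138/514), assuming cohorts of about 38 and 100, full on-site attendance and no early stop; the assumed alternatives run from 15.5% to 30.7%. These are shares of panels and say nothing about how many cases would be missed. The point should be corrected, but it does not threaten case reporting: at the final analysis the effect is limited to Tables 14.3.7.8 and 14.3.7.9, and it matters more at the second interim, where fewer other outputs would show a late case.

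**What to change.** In SAP 6.6.3, build the Hy's Law table on all ALT, AST and total bilirubin values after first dose, including Visit 5 and unscheduled samples, with each component flagged as on- or off-treatment. The on-treatment table can stay as a second panel. State the same period for bilirubin as for ALT and AST in the titles of Tables 14.3.7.8 and 14.3.7.9, and apply the same rule to the second interim table in SAP 8.10.3. For subjects with both elevations, list the dates and flag whether an ALT or AST ≥3×ULN falls on or before a total bilirubin ≥2×ULN; this settles the order that crossing maxima cannot show.

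The cost is one SAP sentence, one programming filter, one flag, one short listing and two table titles. No new data are needed.
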